PROTOCOL TITLE: Implementation of Telemedicine for patients with wounds and ulcers.

1) Protocol Title

Title: Implementation of Telemedicine for patients with wounds and ulcers.

Protocol Version Date: March 11th, 2021

2) Objectives:

The objective of this quality improvement project is to assess if telemedicine can improve the quality of specialty care offered for new patients with wounds and ulcers due to peripheral artery disease (PAD) and diabetes mellitus (DM) at RHCs. The specific aims of this project are:

- a) Implement telemedicine consultations at rural health clinics.
- b) Evaluate the effect of telemedicine consultation to improve time to specialist evaluation and time to definitive treatment for patients with wounds and ulcers in rural clinics.
- c) To determine if patients with lower levels of activation need more resources to help get care when offered telemedicine

Hypothesis: *Telemedicine consultation can decrease mean time to specialist consultation and time to definitive vascular treatment by 50%. Use of telemedicine will be able to overcome low levels of patient activation by allowing patients to get care in their home area.*

3) Background

Each year, more than 185,000 patients with PAD, DM, or combined PAD/DM undergo leg amputation. Costs to treat wounds and ulcers currently approach \$25 billion annually and are expected to double in the next decade.^{1,2} When ulcer treatment is not effective, amputation is the outcome and currently, 1.4 million people live with an amputation in the United States.^{3,4} Predictors of higher amputation rates include worse ankle-brachial index,⁵ African-American race⁶, lower socio-economic status, dialysis dependence, and older age.⁷⁻¹⁰ Patients living in rural areas are 51% more likely to undergo amputation than those in urban areas.^{11,12}

Patients residing in rural areas face numerous barriers to care. Their concerns are poorly understood, however, these patients are typically of lower socioeconomic status and have limited knowledge of chronic diseases which results in lower patient activation. The distance and burden of coordinating travel, time off work, and need to attend multiple clinic visits can be impossible for patients and families. The hardships patients endure in an effort to attend remote appointments results in unrealistic patient expectations, physician dissatisfaction, non-compliance with treatment, increased hospitalizations, and lower patient activation in disease management.

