6. Willing to be contacted by research team

Exclusion Criteria

1. Patients who do not want to participate in the telemedicine visit
2. Adults unable to read and write English. The PAM study is only in English at this time
3. Patients that do not have a home phone or home internet. This is needed to do follow up and any follow up telemedicine visits
4. Patients that do not have a smart phone or computer that can connect to the internet

PROTOCOL TITLE: Implementation of Telemedicine for patients with wounds and ulcers.

We do not plan to include:

- Pregnant women- low incidence of wounds in these patients due to PAD and DM
- Prisoners- Cannot accurately determine care and outcomes

Number of Subjects:

Rural Health Clinic A	25
Rural Health Clinic B	25
Rural Health Clinic C	25
Rural Health Clinic D	25
Rural Health Clinic E	25
Total Number of Patients	125

We plan to include 25 subjects at each of the 5 out of network clinics that are referred to the UC Davis Vascular Clinic for telehealth services for a total enrollment of 125 patients.

5) Study Timelines

The Screening and follow up of data of all patients will start approximately from 5/01/2020 – and end 12/31/2021

Review and Analysis should will be completed by approximately 06/30/2022

6) Study Endpoints

The primary endpoint for this study is time to specialty consultation.

Secondary endpoints are time to revascularization, time to other specialty consultation, time to wound healing, number of telemedicine visits, major amputation, number of hospitalizations, number of emergency room visits, and number of in person visits.

PROTOCOL TITLE: Implementation of Telemedicine for patients with wounds and ulcers.

7) Procedures Involved

Screening: Patients referred from rural clinics will be screened when they are referred to the UC Davis Vascular Clinic for telehealth services to determine if they meet the inclusion/exclusion criteria.

Enrollment/Procedures at Baseline Telehealth Visit: Patients receiving telehealth services will follow the standard operating procedures for those visits. Which includes asking new patients to complete the UCD Privacy statement for new patients and a patient activation questionnaire on the day of their telemedicine visit.

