Follow-Up Post Telehealth Visit: All patients will be contacted every 4 weeks to determine if they have had a procedure for their leg wound (revascularization) and if the wound has healed. Patients will be followed until they reach a secondary study end-point which is wound healing, amputation, or for a maximum of 12 months.

8) Withdrawal of Subjects

Patients who choose not to participate in completing a patient activation questionnaire will not be included in this QI project. Patient care is not directed in this project and is clinical driven per standard of care and standard operating procedures for the Vascular Clinic.

9) Risks to Subjects

This is a minimal risk study and the only risk foreseen is a potential breach of confidentiality which will be minimized by securing the data as outlined in the protocol.

10) Potential Benefits to Subjects

No direct benefits to the patient will occur during the data collection and review of the QI project. Future patients may receive a benefit from increased access to telehealth visits or proven to shorten time to care for patients referred from rural clinics.

PROTOCOL TITLE: Implementation of Telemedicine for patients with wounds and ulcers.

Statistical Analysis Plan: Changed as a result of COVID and removal of the comparison arm of the study

The data will be analyzed by Kaplan-Meier analysis comparing time to specialty visit for patients who underwent telemedicine visits to those who did not. Secondary outcome analysis will include chi-squared analysis of the proportion of patients that had wound healing in the telemedicine group compared to those that did not have a telemedicine visit, and Kaplan-Meier analysis of time to definitive revascularization and wound healing for patients that underwent telemedicine and were treated at UCD.

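### Wound healing is learned of only at 4-weekly contacts but analysed by ordinary Kaplan-Meier, so healing dated at the contact is up to 4 weeks late

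*Combined protocol and SAP*

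**What the plan says.** - **Ascertainment.** Section 7 (Procedures Involved), in its paragraph on follow-up, reads: "All patients will be contacted every 4 weeks to determine if they have had a procedure for their leg wound (revascularization) and if the wound" is healed. Patients are followed to "wound healing, amputation, or for a maximum of 12 months".
- **Analysis.** Statistical Analysis Plan: "Kaplan-Meier analysis of time to definitive revascularization and wound healing for patients that underwent telemedicine and were treated at UCD". It names no method for interval-censored data and no rule for dating an event. Healing is also to be compared as a proportion, by chi-squared test.
- **Status of the endpoints.** Section 6 (Study Endpoints): "The primary endpoint for this study is time to specialty consultation". Healing and revascularization come second: "Secondary endpoints are time to revascularization, time to other specialty consultation, time to wound healing".
- **Hypothesised effect.** Section 2 (Objectives): "Telemedicine consultation can decrease mean time to specialist consultation and time to definitive vascular treatment by 50" percent. No effect on healing time is hypothesised.
- **Baseline.** The only historical time in the document is a median of 9 weeks, and it is for specialist consultation.

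**The concern.** Ordinary Kaplan-Meier treats each event time as exactly known. A procedure has a date of its own, but healing does not. When the only information is whether the wound has closed by a given contact, the time of closure is bracketed by two contacts and no more. Assigning it to the later contact always errs in the late direction.

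At stake are the reported healing curve, its median and any mean healing time. Patients who miss contacts would appear to heal later than they did. The same applies to revascularization only if the contact date were used in place of the procedure date, and the plan does not say which will be used.

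**Working it through.** **1. The plan's own figure.** The only stated figure nearby is 89.2% power for time to consultation (n = 24, HR 3.0, 9-week median, event probability 0.44). Accrual and follow-up are not given, so a fixed follow-up of about 2.5 weeks is solved from the 0.44.

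- Expected events: 24 × 0.44 = 10.56, or 11.
- Per-patient observed events v1 = 0.44. Expected under the historical rate v0 = 0.44/3 = 0.147.
- Power = Φ[(√24 × (0.440 − 0.147) − 1.96 × √0.147) / 0.550] = Φ(1.25) = 89.4%, where 0.550 is the standard deviation of the per-patient difference under the alternative.

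This agrees with 89.2%. No input comes from the 4-weekly contacts, so the dating of healing cannot change it.

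**2. Delay from dating at the contact.** The inputs are the 4-week spacing (section 7) and, as an assumption, exponential healing times with true median *m*. The document gives no *m*, so a range is shown. The clock is taken to start with the contact schedule, and means ignore the 12-month limit.

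- Proportion unhealed: S(t) = 2^(−t/m)
- True mean = m / ln 2
- Mean when dated at the contact = 4 / (1 − S(4))
- Median when dated at the contact = first multiple of 4 at which S ≤ 0.5

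For m = 4.5: S(4) = 0.540 and S(8) = 0.292, so the median reads 8. The means are 4.5/0.693 = 6.49 and 4/0.460 = 8.70.

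| True median (weeks, assumed) | Median as dated | True mean | Mean as dated | Mean delay | Delay / true mean |
|---|---|---|---|---|---|
| 4.5 | 8 | 6.49 | 8.70 | 2.20 | 33.9% |
| 9 | 12 | 12.98 | 15.09 | 2.10 | 16.2% |
| 13 | 16 | 18.76 | 20.83 | 2.07 | 11.0% |
| 26 | 28 | 37.51 | 39.55 | 2.04 | 5.4% |
| 40 | 40 | 57.71 | 59.73 | 2.02 | 3.5% |

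Delays are differences taken before rounding. The absolute delay hardly depends on *m*, but the relative delay depends on it strongly.

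**3. Missed contact.** One missed contact widens the bracket to 4 + 4 = 8 weeks. The delay can then reach 8 weeks, and averages about 8/2 = 4 if closure is roughly uniform over the bracket. The document gives no rate of missed contacts.

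**4. What stays correct.** With regular contacts from a common origin, everyone healed by week 4 is counted at week 4, and so on. The contact-dated curve at weeks 4 and 8 is 0.540 and 0.292 in the example, which are the true values. The error lies between contacts, in the median and in the mean.

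**5. Midpoint dating.** Moving each event back 2 weeks leaves a mean error of 2.20 − 2 = 0.20 week at m = 4.5 and 2.04 − 2 = 0.04 week at m = 26.

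**The case against.** The strongest reply is that this is a matter of reporting resolution on a secondary endpoint followed for up to 12 months. With regular contacts Kaplan-Meier is right at each contact, and Turnbull would give the same values there. The chi-squared comparison of proportions healed barely depends on dating within a 4-week window. All of that stands, and it limits the point. It does not remove it, because the plan promises time to healing, and a median or mean read from contact dates is late.

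A reader might infer more than the documents support:

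- **That both events are recorded only as yes or no.** The text is silent on dates; it does not say they go unrecorded. The revascularization curve is limited to patients treated at UCD, whose procedure dates should be in the institution's records.
- **That a true 50% reduction in time to revascularization would look like 11%.** This borrows the 9-week consultation median: half is 4.5, which reads as 8, and (9 − 8)/9 = 11%. But the hypothesis is worded in means, and on means the apparent reduction is 1 − 8.70/12.98 = 33%. The median figure is also an accident of alignment. A baseline of 7.9 weeks gives S(4) = 0.496 and a dated median of 4, so (7.9 − 4)/7.9 = 49%. A baseline of 15 weeks (true median 7.5, read as 8) gives (15 − 8)/15 = 47%.
- **That a planned comparison is diluted.** No comparator is named for these curves, and healing has no hypothesised effect.

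The documents also do not fix time zero for these endpoints. If time runs from referral, contact dates are staggered between patients. The steps would not fall only at weeks 4, 8 and 12, and the reassurance about the contact times would weaken. Each event would still be dated 0 to 4 weeks late.

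**Conclusion.** The point holds for wound healing. Followed as written, with healing dated at the contact, times are late by 0 to 4 weeks, about 2 weeks on average (2.0 to 2.2 over assumed true medians of 4.5 to 40 weeks, exponential times), and later after a missed contact. The median is rounded up to a contact date. For revascularization the gap is one of missing detail: the plan should say which date is used.

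The error cannot be called large against the plan's hypothesised effect. Its relative size depends on baseline times that the document does not give: under the assumptions above it runs from 33.9% of the true mean down to 3.5%. The primary endpoint and its 89.2% power are unaffected. The change is worth making because it is cheap and the method it replaces assumes exact times that the stated follow-up does not supply.

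**What to change.** - **Healing.** At the existing contacts, record the date of the last one with the wound open and the first with it closed. In the Statistical Analysis Plan, replace ordinary Kaplan-Meier for time to healing with an interval-censored estimate (Turnbull). At the least, add midpoint dating as a sensitivity analysis.
- **Revascularization.** State that the event time is the actual procedure date from the UCD record, not the date of the contact at which it was reported. Kaplan-Meier then applies as planned.

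The contact schedule is unchanged. The cost is two dates per patient from contacts already planned, a look-up in the procedure record and a sentence or two in the analysis plan. The small downside is an estimator less familiar to readers than Kaplan-Meier.

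### Follow-up ends at the first recorded wound healing, with no confirmation and no event-date rule, so a false or short-lived healing cannot be corrected

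*Combined protocol and SAP*

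**What the plan says.** Section 7, under Follow-Up Post Telehealth Visit, gives the whole procedure for ascertaining healing. Contact is made with every patient at 4-week intervals, and its purpose is to find out whether revascularization has taken place "and if the wound has healed". The next sentence sets the end of observation: "Patients will be followed until they reach a secondary study end-point which is wound healing, amputation, or for a maximum of 12 months".

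The mode of contact is not stated there. Section 4, exclusion item 3, excludes patients without a home phone or home internet and explains: "This is needed to do follow up and any follow up telemedicine visits". That implies remote contact.

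Section 6 lists time to wound healing among the secondary endpoints. The Statistical Analysis Plan uses healing twice. One use is a "chi-squared analysis of the proportion of patients that had wound healing in the telemedicine group" against patients without a telemedicine visit. The other is a "Kaplan-Meier analysis of time to definitive revascularization and wound healing for patients that underwent telemedicine and were treated at UCD".

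The documents do not define healing, say who judges it, require that it be confirmed or sustained, or say which date enters the Kaplan-Meier analysis.

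**The concern.** Asking about healing at intervals is ordinary in a project of this kind. The difficulty is that the same observation both records the event and stops further observation. If a patient reports a scabbed ulcer as healed, or the ulcer reopens two weeks later, no further contact is planned at which this could come to light. Each contact with an unhealed wound is a new opportunity for such an error, and the stopping rule makes each one permanent.

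Two results are exposed. The healed proportion can only be pushed upward by false or transient healings. The Kaplan-Meier estimate can be moved in either direction: false reports create events that are too early or should not exist, while dating a true healing at the contact that discovers it makes the event too late.

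**Working it through.** **The plan's own figure.** The documents give no number for healing. The only power statement concerns time to specialist consultation, and it reproduces. Expected events are 24 × 0.44 = 10.56, stated as 11. A two-sided one-sample log-rank test using (O − E)/√E, with control hazard ln 2/9 per week and hazard ratio 3.0, has 89.4% power with no accrual period and 90.0% with accrual throughout. Simulation gives 89.3%. The stated value is 89.2%. This neither supports nor weakens the point about healing.

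**Inputs for healing.** From section 7: contact every 4 weeks, for at most 12 months, so 52/4 = 13 contacts at most. Assumed, because the documents give no value: a probability p that an unhealed wound is recorded as healed at a given contact, taken as 1%, 2%, 3% and 5%, with errors independent between contacts.

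**False healing under the current rule.** For a wound that never heals and is followed for the full period, P(at least one false report) = 1 − (1 − p)^13.

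**False healing with confirmation.** Requiring two consecutive reports, the probability of at least one run of two in 13 contacts follows from a contact-by-contact recursion. It is close to 12p², since there are 12 adjacent pairs.

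| p per contact | One report suffices, 13 contacts | One report suffices, 12 contacts | Two consecutive reports, 13 contacts |
|---|---|---|---|
| 1% | 12.2% | 11.4% | 0.1% |
| 2% | 23.1% | 21.5% | 0.5% |
| 3% | 32.7% | 30.6% | 1.0% |
| 5% | 48.7% | 46.0% | 2.8% |

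Counting 12 or 13 contacts makes little difference.

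**Sensitivity to independence.** If a patient who misjudges the wound always does so, the cumulative error is simply p, that is 1% to 5%, and a second report from the same patient removes none of it. The truth lies somewhere between this and the table.

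**Effect on the healed proportion.** The table applies only to never-healing wounds. If 30% of wounds were of that kind (assumed), the inflation would be 0.30 × 12.2% = 3.7 to 0.30 × 48.7% = 14.6 percentage points under independence, and 0.30 × 1% = 0.3 to 0.30 × 5% = 1.5 points under full correlation.

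**Reopening.** If 5% to 30% of healed wounds reopen (assumed), a recorded 50% healed corresponds to 50% × 0.95 = 47.5% down to 50% × 0.70 = 35% with sustained healing. One confirming contact would catch only reopenings that occur before it.

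**Dating.** If the contact date is taken as the event date, the delay for a true healing lies between 0 and 4 weeks. A uniform time within the interval gives a mean of 4/2 = 2 weeks. For an exponential healing time with hazard λ the mean delay is 4/(1 − e^(−4λ)) − 1/λ, which is 2.1 weeks for an assumed median of 8 weeks and 2.0 weeks for 36 weeks.

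**The case against.** The strongest reply is that much of the concern comes from silence. Four stronger readings are tempting, and the documents support none of them.

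- *Healing rests solely on the patient's unverified word.* Section 7 says that contact is made to determine healing; it does not say that the patient's answer is the only source. Section 3 says the study will examine information collected at telehealth visits, and sections 4 and 6 anticipate follow-up telemedicine and in-person visits. Clinical views of the wound may exist. What can be said is that none is required for, or linked to, the healing endpoint.
- *Healing is dated late.* No text makes the contact date the event date, and asking for the closure date is compatible with the plan. The lateness is conditional, and the net effect on the Kaplan-Meier curve is unknown because false reports pull the other way.
- *Between 12% and 49% of unhealed wounds will be misrecorded.* These figures rest on assumed error rates, on independence, and on wounds that never heal and are followed for all 12 months. Twelve months is a maximum, and section 5 ends follow-up on 12/31/2021, so late enrollees may have fewer contacts.
- *A clinician-read photograph should be mandatory because section 3 reports high concordance of remote images.* That statement concerns physicians viewing images at remote consultation in programmes abroad, not patient-sent pictures used to verify closure. Exclusion item 4 is met by any smart phone or internet-capable computer, so a camera is not guaranteed, and staff time would be needed.

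Two further points are fair. Healing is a secondary endpoint in a minimal-risk quality improvement project. The chi-squared comparison also has a prior problem: it needs a group without telemedicine, although the Statistical Analysis Plan's own heading says the comparison arm was removed.

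What survives is the stopping rule. It is written in the protocol, not inferred, and whatever the source of the healing report, the planned follow-up provides no later contact that could overturn it.

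**Conclusion.** The point holds in a limited form. Healing is ascertained on a 4-week grid, needs no confirmation, has no dating rule, and closes follow-up when first recorded. A false or transient healing therefore enters both healing analyses as a final success. The direction of the bias in the healed proportion is clear (upward); its size is not, because the documents give no error or reopening rate. The 12% to 49% range is best read as an illustration under independence, and it falls to 1% to 5% under full within-patient correlation. The delay of about 2 weeks, at most 4, applies only to true healings and only if the contact date is used.

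The primary endpoint, time to specialty consultation, and its power statement are untouched. This is an inexpensive improvement to a secondary endpoint, not a threat to the main result.

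**What to change.** 1. Count healing only if the wound is reported closed at one 4-weekly contact and still closed at the next scheduled contact.
2. Amend the follow-up sentence in section 7 so that a first report of healing does not end follow-up before that confirming contact.
3. State the event date in the Statistical Analysis Plan. Either use the closure date reported by the patient, or treat healing as interval-censored between the last contact with an open wound and the first of the two contacts with a closed one. The second option avoids relying on a recalled date. For revascularization, use the procedure date.
4. Where a telemedicine or clinic visit already provides a view of the wound, use it as supporting evidence. Do not require a new clinician-read photograph.
5. Say how a first report without a confirming contact is handled, for example as not healed in the main analysis and healed in a sensitivity analysis.

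The cost is at most one more contact per healed patient within the existing schedule, plus one more item to record. The downside is that some healings near the end of follow-up will stay unconfirmed, so the healed proportion will be somewhat lower. If errors are strongly correlated within patients, the confirming report will remove fewer of them than the table suggests.

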
In February 2016 focused guidelines for assessment of ulcers were published as a joint effort by the Society for Vascular Surgery, American Podiatric Medical Society, and Society of Vascular Medicine. Implementation of these guidelines

PROTOCOL TITLE: Implementation of Telemedicine for patients with wounds and ulcers.

has been poor, especially in rural areas. Telemedicine improves access to expert specialty consultation and patient-centered care in the ambulatory settings. Implementation of telemedicine combines involved faculty with a team-building mentality, concise web-based tools for incorporation into daily practice, and specialty consultation. Telemedicine has been effective in psychiatry, pediatrics, dermatology, and cardiovascular diseases. In telemedicine wound programs for the treatment of ulcers in other countries, physicians found images at remote consultation showed a high concordance compared to in-person evaluation and providers were successful at making wound care recommendations based on images.

The NHLBI strategic vision prioritized community-based effectiveness and implementation research strategies to address health inequalities. Multiple countries have implemented telemedicine wound care programs to improve cost effectiveness of treatment. These programs decreased costs for transportation to provide wound care by 46%. Extrapolation to US wound care costs could indicate a potential savings of nearly \$15 billion annually by implementing a national telemedicine treatment program for ulcer management.

The Vascular Clinic at UC Davis currently conducts telehealth medical visits as a part of the general referral program at UC Davis Health. Within this referral program the clinic works with several Rural Health Centers (RHC) in California and utilizes telehealth medicine as a part of the referral process. This research study proposes to examine the information that is collected during these visits the primary endpoint for this study is time to specialty consultation

4) Inclusion and Exclusion Criteria

Patients will be identified by the clinic when they come in for their regular visit.

Inclusion Criteria

1. 18 years or older
2. Have a wound or ulcer for more than two weeks.
3. Have a diagnosis of Diabetes Mellitus (DM), Peripheral Artery Disease (PAD), vascular disease, or combined PAD/DM
4. Willing to see a provider by telemedicine
5. Able to complete the Patient Activation Measurement (PAM) survey

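### The SAP keeps a chi-squared comparison of wound healing with patients who had no telemedicine visit, although the comparison arm was removed and no healing comparator is defined

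*Combined protocol and SAP*

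**What the plan says.** The heading of the Statistical Analysis Plan describes it as "Changed as a result of COVID and removal of the comparison arm of the study". The paragraph under that heading sets out three analyses:

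- Time to specialty visit: "The data will be analyzed by Kaplan-Meier analysis comparing time to specialty visit for patients who underwent telemedicine visits to those who did not".
- Healing: a chi-squared analysis of the "proportion of patients that had wound healing in the telemedicine group compared to those that did not have a telemedicine visit".
- Time to event in one group: "Kaplan-Meier analysis of time to definitive revascularization and wound healing for patients that underwent telemedicine and were treated at UCD".

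The next paragraph, on sample size, names a two-sided one-sample log-rank test for time to consultation against a historical median of 9 weeks. It assumes a Weibull distribution with shape 1 and a hazard ratio of 3.0, and states 89.2% power with 24 patients.

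Section 6 lists time to wound healing as a secondary endpoint. Section 7 ends follow-up at healing, at amputation or at 12 months.

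**The concern.** A chi-squared comparison of proportions needs healed and unhealed counts in two groups. The plan supplies one group. Whoever runs the analysis must find the second group elsewhere and decide which patients, which period and which definition of healing to use. Those decisions could be made after the telemedicine results are known. A statement that telemedicine improves healing would then rest on a reference that the plan never specified, and a reader could not tell whether it had been fixed in advance.

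Two smaller points follow from the same removal of the comparison arm. The sentence on time to specialty visit still reads as a two-group comparison, although the next paragraph specifies a one-sample test. And the section 2 hypothesis of a 50% reduction in time to vascular treatment has no reference time, while the revascularization analysis is single-arm.

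**Working it through.** **1. Who is enrolled.** Section 4 includes only patients who are "Willing to see a provider by telemedicine" and excludes "Patients who do not want to participate in the telemedicine visit". It plans 25 patients at each of 5 clinics, 5 × 25 = 125, all referred for telehealth. Section 7 has new patients complete "a patient activation questionnaire on the day of their telemedicine visit". Section 8 adds: "Patients who choose not to participate in completing a patient activation questionnaire will not be included in this QI project". Together these imply 125 telemedicine patients and 0 without a telemedicine visit. This is an inference; no section states an allocation.

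**2. What the healing test needs.** Let a and b be healed and unhealed telemedicine patients, and c and d the same counts without telemedicine, with N = a + b + c + d. Then

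X² = N(ad − bc)² / [(a+b)(c+d)(a+c)(b+d)].

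With c = d = 0, both numerator and denominator are 0, so the statistic is undefined.

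**3. Whether an outside reference fills the gap.**

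| Outcome | Historical reference in the documents |
|---|---|
| Time to consultation | 9-week median, Weibull shape 1 |
| Proportion healed | none |
| Time to revascularization or definitive treatment | none |

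The historical controls in the sample-size paragraph are described only for time to consultation. They carry no healing data.

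**4. Which test the stated power belongs to.** Inputs from the sample-size paragraph: n = 24, hazard ratio 3.0, two-sided 5%, event probability 0.44.

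- Reference hazard: ln 2 / 9 = 0.0770 per week. Telemedicine hazard: 3 × 0.0770 = 0.2310 per week.
- Expected events: 24 × 0.44 = 10.56, rounded to 11, as stated.
- The follow-up behind this calculation is not given. Solving 1 − exp(−0.2310 t) = 0.44 gives t of about 2.51 weeks, if follow-up is common to all patients (inferred).
- Statistic (O − E)/√E. Per patient under the alternative, mean O is 0.44 and mean E is 0.44/3 = 0.1467, a difference of 0.2933. The variance of O − E under the alternative is 0.3027 (SD 0.5502).
- Power = Φ[(0.2933 × √24 − 1.96 × √0.1467) / 0.5502] = Φ[(1.437 − 0.751) / 0.5502] = Φ(1.248) = 0.894. Simulation with 300,000 runs gives 0.893. The plan states 0.892.

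The stated power is thus reproduced by the one-sample test. This confirms the arithmetic only. At the 12-month maximum follow-up, the event probability at hazard ratio 3.0 would exceed 0.99, not 0.44. That is a separate question.

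**5. What one arm can deliver on healing.** The 95% CI half-width for a proportion is widest at 0.5. With 125 independent patients it is at most 1.96 × √(0.25/125) = 0.088, or 8.8 percentage points. Any reference further than that from the observed proportion would lie outside this interval. A reference chosen afterwards could therefore decide the conclusion.

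**The case against.** The best defence is that the patients without a telemedicine visit are the historical controls of the sample-size paragraph, and that the listed secondary endpoint, time to wound healing, already has a single-arm Kaplan-Meier analysis. The second part stands: healing can be analysed, and only the comparative test lacks a basis. The first part works for time to consultation but not for healing, because those controls exist only as an assumed median and distribution for consultation time.

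It can also be said that the 50% reduction is a hypothesis and not a planned test, so no analysis step breaks. That is fair, and it is why the point is only a note here.

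Two stronger readings are tempting, and the documents support neither.

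- A reader might infer that the primary endpoint has no usable analysis. It has one. The SAP commits to the one-sample log-rank test, and its reference curve is fully set by the 9-week median and shape 1. Kaplan-Meier is an estimator, and no two-sample test is named for this endpoint. The mismatch is one of wording.
- A reader might infer that a two-group version would be badly underpowered with 11 events. Those 11 events are 24 × 0.44, all in the telemedicine sample. No control number, allocation ratio or patient-level control data are given, so the documents support no two-group power figure.

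Simply dropping the chi-squared test in favour of the planned Kaplan-Meier analysis is not enough either. That analysis is limited to patients treated at UCD, which may be fewer than all telemedicine patients. And because amputation ends follow-up, censoring amputations would treat those patients as still able to heal and would overstate cumulative healing.

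**Conclusion.** The concern holds for the healing comparison, which cannot be run as written. It has 0 of 125 planned patients in the second group and no external reference to put in their place. The zero rests on reading sections 4, 7 and 8 together; the missing healing reference is a plain reading of the documents. The SAP heading introduces the current, changed plan, so this is not superseded text.

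The scope is one secondary analysis and any comparative claim built on it. The wording on time to specialty visit and the missing reference for time to treatment are minor. This should be corrected before analysis, but it does not threaten the primary test or its stated power.

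**What to change.** In the Statistical Analysis Plan:

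- Delete the chi-squared comparison. Report the proportion healed among all enrolled telemedicine patients with a 95% CI, counting amputation before healing as not healed.
- Keep the time-to-healing analysis, but treat amputation as a competing event (cumulative incidence of healing) and state the population: all telemedicine patients or only those treated at UCD.
- State the time horizon for the proportion and how incomplete follow-up is counted. Section 5 ends follow-up on 12/31/2021, so patients enrolled after 12/31/2020 cannot reach 12 months.
- Make no comparative healing claim unless a historical healing reference already exists and is cited before analysis.

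Minor edits: reword the sentence on time to specialty visit as the one-sample log-rank test against the 9-week historical median, shown with the telemedicine Kaplan-Meier curve. Treat the 50% reduction in time to vascular treatment as descriptive unless an existing reference time is cited before analysis.

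The cost is SAP and hypothesis wording, with no new patients or data collection. Citing a historical reference is optional extra work. The downside is that healing and time to treatment become descriptive, which is all that the single-arm design supports.
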